2.3.4 Prior, concomitant and post therapies

Concomitant medications will be coded using WHO Drug coding dictionary, summarized, and listed. The summary of concomitant medications will show the number and percentage of subjects taking concomitant medications by Ingredient. Multi-ingredient products will be summarized by their separate ingredients rather than as a combination of ingredients. Anatomical Therapeutic Chemical (ATC) classification Level 1 (Body System) information will be included in the data listing only. In order to be considered a concomitant medication, the concomitant medication must have been taken at some point during the on-therapy window.

Prior anti-cancer therapy will be coded using WHO Drug coding dictionary, then summarized by type of therapy and listed. Separate tables will be produced displaying prior medications by ingredient (counting multiple ingredients taken as part of a combined treatment on separate rows) and displaying combination regimens as single rows e.g. cisplatin + gemcitabine. Combined regimens will be defined based on common start dates of each ingredient, which are entered separately on the eCRF. A summary of the number of prior anti-cancer therapy regimens will also be produced.

Prior anti-cancer radiotherapy and prior cancer and non-cancer surgical procedures will be listed.

The number and percentage of subjects that received chemotherapy, immunotherapy, hormonal therapy, biologic therapy, radioactive therapy, small molecule targeted therapy, radiotherapy and cancer-specific surgery as post study treatment anti-cancer therapy will be summarized.

Summary statistics for the time from study treatment discontinuation to the first post study treatment anti-cancer therapy (in weeks) will also be included in this summary table.

Follow-up anti-cancer therapy will be coded using WHO Drug coding dictionary, then summarized by ingredient. A listing of the type of follow-up anti-cancer therapy received (chemotherapy, immunotherapy, hormonal therapy, biologic therapy, radioactive therapy, small molecule targeted therapy) and details of the anti-cancer therapy for each subject will be provided.

Anti-cancer radiotherapy and both cancer- and non-cancer related surgical procedures will be listed separately.

2.3.5 Protocol Deviations

Protocol deviations identified during the study are reviewed by the study team. During this review, deviations are classified as important or not important based on their impact on data reliability and/or patient safety, wellbeing or rights.

Important protocol deviations including inclusion/exclusion criteria deviations will be summarized. A separate summary of inclusion/exclusion criteria deviations will also be provided. All important protocol deviations will be listed. Following the COVID-19 pandemic, separate tables will be created to display the protocol deviations related to COVID-19 and those not related to COVID-19. Deviations related to COVID-19 will be classified as important to ensure transparent presentation of the impact of the pandemic in the clinical study report. Where applicable, the relationship of a protocol deviation to COVID-19 will be displayed in the listing.

Deviations will not result in subject exclusion from any population. However, for protocol deviations that are deemed by clinical team as having a significant impact on the interpretation of the efficacy results (e.g. subject with incorrect histologic type enrolled), sensitivity analysis for efficacy may be conducted by excluding subjects with such deviations.

2.4 Analysis of the primary objective

The analyses of the primary endpoint will take place once all patients have either died or been transitioned off the study. The primary analysis population for efficacy analyses is ITT. The BRAF V600E population will be used for supportive analyses of efficacy. Summaries of primary endpoint results may be provided for the primary analysis cohort, the expansion cohort and primary and expansion cohorts combined.

2.4.1 Primary endpoint

The primary efficacy assessment will be the evaluation of overall response rate (ORR) calculated as a proportion of the subjects who have a confirmed response relative to the total number of subjects in the analysis population. Clinical response to dabrafenib in combination with trametinib will be assessed according to the appropriately established response criteria for each histologic cohort. [Table 2-1](#) outlines the response criteria and subcategories for overall response for each histologic cohort. Following feedback on the WHO Grade 1 and 2 Glioma cohort from the FDA, additional summaries of best response and duration of response will be produced excluding Minor Response (MR) from the subcategories defined as Response for this cohort.

Table 2-1 Response Criteria and Definition of Response by Histology

Histology	Response Criteria	Response Subcategories defined as Overall Response
ATC, BTC, GIST, ASI	RECIST 1.1	CR, PR
NSGCT/NGGCT	RECIST 1.1; Serum tumor markers normalization or not will be considered as part of response criteria (serum tumor markers: AFP, β -HCG)	Marker-Negative CR (CR-), Marker-Positive CR (CR+), Marker-Negative Partial Remission (PR-), Marker-Positive Partial Remission (PR+)
WHO Grade 1 and 2 Glioma	Response Assessment Criteria for WHO Grade 1 or 2 Glioma: RANO Working Group	CR, PR, MR
WHO Grade 3 and 4 Glioma	Updated Response Assessment Criteria for WHO Grade 3 or 4 Glioma: RANO Working Group	CR, PR
MM	IMWG Uniform Response Criteria for MM	sCR, CR, PR, VGPR
HCL	Adapted from NCCN guidelines, Consensus Resolution Criteria and previous studies definition	CR without MRD (CR-MRD), CR with MRD (CR+MRD), PR

Abbreviations: AFP, alpha-fetoprotein; ASI, adenocarcinoma of the small intestine; ATC, anaplastic thyroid cancer; β -hCG, beta-human chorionic gonadotropin; BTC, biliary tract cancer; CR, complete response; GIST, gastrointestinal stromal tumor; HCL, hairy cell leukemia; IMWG, International Myeloma Working Group; MM, multiple myeloma; MR, minor response; MRD, minimal residual disease; NCCN, National Comprehensive Cancer Network; NGGCT, non-geminomatous germ cell tumor; NSGCT, non-seminomatous germ cell tumor; PR, partial response; RANO, Response Assessment for Neuro-Oncology; RECIST, Response Evaluation Criteria in Solid Tumors; sCR, stringent complete response; VGPR, very good partial response; WHO, World Health Organization

The best confirmed overall response is the best confirmed response recorded from the start of treatment until disease progression or start of new anti-cancer therapy, whichever earlier, and will be determined programmatically based on investigator assessment at each time point.

If there are two assessments separated by not evaluable (NE) assessment(s) the best response shall be assessed applying the algorithm below, collapsing data by ignoring NE assessments.

Subjects with best response of Not Evaluable (NE), unknown or missing will be considered non-responders; i.e. they will be included in the denominator when calculating the percentage.

The first assessment may occur before the first planned assessment. Confirmation of response may be based on planned and/or unscheduled assessments.

Table 2-2, Table 2-3, and Table 2-4 below outline the programming algorithm used to define confirmed response for each of the histologic cohorts.

Table 2-2

**Confirmed Response Criteria for Solid Tumors following RECIST 1.1
(ATC, BTC, GIST, ASI, NSGCT/NGGCT) or RANO (WHO Grade 1&2
Glioma, WHO Grade 3&4 Glioma)**

Confirmed Response Category	Criteria for Definition of Confirmed Response

CR, PR, MR, CR-, CR+, PR- and PR+.
 
(MR only applicable for WHO Grade 1&2 glioma)
 
(CR-, CR+, PR-, and PR+ only applicable to NSGCT/NGGCT)
	
 • Two consecutive assessments are required. A confirmatory disease assessment should be performed no less than 4 weeks (28 days) from the time of initial CR, PR, MR, CR-, CR+, PR- or PR+. If a response of any type is assessed and the consecutive assessment is a response of lower magnitude then the confirmed response corresponds with the latter assessment which is the response of lower magnitude. For example, a CR followed by PR results in a confirmed PR response. • If there is 1 assessment within this category, the timing of this assessment is less than 6 weeks after the first dosing and all other assessments are either NE, missing or not done then the confirmed response is NE. • Confirmed responses in this category cannot be assigned for assessments after a patient has an overall response assessment of PD. • For NSGCT/NGGCT, ordering of response magnitude from high to low is CR-, CR+, PR-, PR+. For WHO Grade 1&2 glioma, ordering of response magnitude from high to low is CR, PR, MR. For all other solid tumors, the ordering of response magnitude from high to low is CR, PR.
SD	
 • SD does not need to be confirmed by a second assessment if the disease assessment meets the SD criteria after first dose of study drug at a minimum interval of 6 weeks (42 days). No further minimum window adjustment for assessment will be permitted. If the minimum time for SD is not met, the best response will depend on the subsequent assessments or will be NE. For example, if an assessment of SD is followed by PD and SD does not meet the minimum time requirement for SD, the best response will be PD. When the only assessment (other than NE) after initiation of treatment is SD and the minimum time of 6 weeks from first dose of study drug is not met, the best confirmed response is NE. • If an assessment in the following categories (CR, PR, MR, CR-, CR+, PR- and PR+) is followed by SD or PD, and the timing of the initial assessment is greater than or equal to 6 weeks after the first dosing, then the confirmed response is SD. • If there is 1 assessment in the following categories (CR, PR, MR, CR-, CR+, PR- and PR+) and the timing of the assessment is greater than or equal to 6 weeks after the first dosing, and consecutive assessments are either missing, not done or NE then the confirmed response is SD. • Confirmed responses in this category cannot be assigned for assessments after a patient has an overall response assessment of PD.
PD	
 • PD does not need to be confirmed by a second assessment of PD to confirm PD as the best response. When the only assessment (other than NE) at any point after initiation of treatment is PD the confirmed response is PD.
NE	
 • When a confirmation (of any above category except SD and PD) cannot be made due to lack of assessments the confirmed response is NE.

	
 • If there is 1 assessment in the following categories (CR, PR, MR, CR-, CR+, PR- and PR+) and the timing of the assessment is less than 6 weeks after the first dosing, and consecutive assessments are either missing, not done or NE then the confirmed response is NE. • If all assessments were NE or missing then the confirmed response is NE. • If only non-measurable disease exists at baseline and the response is given as Non-CR/Non-PD then the confirmed response is NE.
--	---

Table 2-3 Confirmed Response Criteria for MM

Confirmed Response Category	Criteria for Definition of Confirmed Response
sCR, CR, VGPR, PR, Minimal Response (MnR), SD	
 • Two consecutive assessments are required. At least one day of separation between two consecutive assessments is required to confirm response. • If a response of any type is assessed and the consecutive assessment is a response of lower magnitude then the confirmed response corresponds with the latter assessment which is the response of lower magnitude. For example, a PR followed by MnR results in a confirmed MnR response, or a PR followed by SD results in a confirmed SD. Two consecutive assessments of SD will constitute a confirmed SD. • If there is 1 assessment and consecutive assessments are either missing or not done then the confirmed response is NE. • The ordering of response magnitude from high to low is sCR, CR, VGPR, PR, MnR SD. • Confirmed responses in this category cannot be assigned for assessments after a patient has an overall response assessment of PD.
PD	
 • PD does not need to be confirmed by a second assessment of PD to confirm PD as the best response. When the only assessment (other than NE) at any point after initiation of treatment is PD the confirmed response is PD.
NE	
 • When a confirmation (of sCR, CR, VGPR, PR, MnR or SD) cannot be made due to lack of assessments the confirmed response is NE. For example, if there is 1 assessment in the following categories (sCR, CR, VGPR, PR, MnR, SD) and consecutive assessments are either missing, not done or NE then the confirmed response is NE. • If all assessments were NE or missing then the confirmed response is NE.

Table 2-4 Confirmed Response Criteria for HCL

Confirmed Response Category	Criteria for Definition of Confirmed Response
CR-MRD, CR+MRD, PR, MR	
 • Two consecutive assessments are required. A confirmatory disease assessment should be performed no less than 4 weeks (28 days) from the time of initial CR - MRD, CR + MRD, PR or MR. • If a response of any type (CR-MRD, CR+MRD, PR, MR) is assessed and the consecutive assessment is a response of lower magnitude then the confirmed response corresponds with the latter assessment which is the response of lower magnitude. For example, a PR followed by MR results in a confirmed MR response. • The ordering of response magnitude from high to low is CR- MRD, CR+ MRD, PR, MR. • Confirmed responses in this category cannot be assigned for assessments after a patient has an overall response assessment of PD.
SD	
 • SD does not need to be confirmed by a second assessment if the disease assessment meets the criteria after first dose of study drug at a minimum interval of 4 weeks (28 days). If the minimum time for SD is not met, the best response will depend on the subsequent assessments or will be NE. For example, if an assessment of SD is followed by PD and SD does not meet the minimum time requirement, the best response will be PD. When the only assessment (other than NE) after initiation of treatment is SD and the minimum time for SD is not met, the best confirmed response is NE. • If an assessment in the following categories (CR-MRD, CR+MRD, PR, MR) is followed by SD or PD, and the timing of the initial assessment is greater than or equal to 4 weeks after the first dosing, then the confirmed response is SD. • If there is 1 assessment in the following categories (CR-MRD, CR+MRD, PR, MR) and the timing of the assessment is greater than or equal to 4 weeks after the first dosing, and consecutive assessments are either missing, not done or NE then the confirmed response is SD. • Confirmed responses in this category cannot be assigned for assessments after a patient has an overall response assessment of PD.
PD	
 • PD does not need to be confirmed by a second assessment of PD to confirm PD as the best response. When the only assessment (other than NE) at any point after initiation of treatment is PD the confirmed response is PD.
NE	
 • When a confirmation (of CR-MRD, CR+MRD, PR or MR) cannot be made due to lack of assessments the confirmed response is NE. • If there is 1 assessment in the following categories (CR-MRD, CR+MRD, PR, MR) and the timing of the assessment is less than 4 weeks after the first dosing, and consecutive assessments are either missing, not done or NE then the confirmed response is NE.

Confirmed Response Category	Criteria for Definition of Confirmed Response
	

• If all assessments were NE or missing then the confirmed response is NE.

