- bone marrow plasma cell percentage (the absolute % must be $\geq 10\%$) – only for subjects without measurable serum and urine M-protein levels and without measurable disease by FLC level

- definite development of new bone lesions or soft tissue plasmacytomas or definite increase in the size of existing bone lesions or soft tissue plasmacytomas
 - development of hypercalcemia (corrected calcium >11.5 mg/dL or 2.65 mmol/L) that can be attributed solely to the plasma cell proliferative disorder
- a. All response categories (CR, sCR, VGPR, PR, MR and PD) require 2 consecutive assessments made at any time before the institution of any new therapy; CR, sCR, VGPR, PR, MR, and SD categories also require no known evidence of progressive or new bone lesions if radiographic studies were performed. VGPR and CR categories require serum and urine studies regardless of whether disease at baseline was measurable on serum, urine, both, or neither. Radiographic studies are not required to satisfy these response requirements. Bone marrow assessments need not be confirmed. For PD, serum M- component increases of more than or equal to 1 g/dL are sufficient to define relapse if starting M-component is ≥ 5 g/dL.
- b. Clarifications to IMWG criteria for coding CR and VGPR in subjects in whom the only measurable disease is by serum FLC levels: CR in such subjects indicates a normal FLC ratio of 0.26 to 1.65 in addition to CR criteria listed above. VGPR in such subjects requires a >90% decrease in the difference between involved and uninvolved FLC levels.
- c. Clarifications to IMWG criteria for coding PD: Bone marrow criteria for PD are to be used only in subjects without measurable disease by M protein and by FLC levels; “25% increase” refers to M protein, FLC, and BM results, and does not refer to bone lesions, soft tissue plasmacytomas, or hypercalcemia and the “lowest response value” does not need to be a confirmed value.

References:

Durie BGM, Harousseau J-L, Miguel JS, et. al. International uniform response criteria for multiple myeloma. *Leukemia*. 2006;20:1467-73.

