2.4.3 Handling of missing values/censoring/discontinuations

Response assessments occurring after disease progression or the start of new anti-cancer therapy will not be included in the determination of best response. Response assessments occurring after end of study treatment but before disease progression or the start of new anti-cancer therapy will be included. There will be no imputation of missing values.

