2.12 Interim analysis

Interim analyses have been carried out to monitor efficacy and safety at regular intervals through the study enrollment and for health authority submission and publication after the end of enrollment. Details of interim analyses are given in section 18.3.2 of the protocol and the interim reporting and analysis plans.

3 Change to protocol specified analyses

No changes were made to analyses specified in the protocol.

4 Appendix

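### SAP Table 2-3 accepts a single PD assessment in multiple myeloma where protocol Appendix 15 requires two, and the SAP does not declare the difference

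*SAP*

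**What the plan says.** **SAP.** Table 2-1 names "IMWG Uniform Response Criteria for MM" as the MM response criteria. Best confirmed response "will be determined programmatically based on investigator assessment at each time point" (section 2.4.1). Table 2-3 requires two consecutive assessments for every MM category from sCR down to SD. The PD row is the exception: "PD does not need to be confirmed by a second assessment of PD to confirm PD as the best response". For the response categories the table adds: "Confirmed responses in this category cannot be assigned for assessments after a patient has an overall response assessment of PD". Section 2.4.3 gives the same cut-off in general terms: "Response assessments occurring after disease progression or the start of new anti-cancer therapy will not be included in the determination of best response". Section 4.3 says that the MM assessment is the investigator's entry on the VISIT form. Section 3 states: "No changes were made to analyses specified in the protocol".

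**Protocol.** Table 8 in section 7.5.2.3 refers MM response to Appendix 15. Note a of that appendix reads: "All response categories (CR, sCR, VGPR, PR, MR and PD) require 2 consecutive assessments made at any time before the institution of any new therapy". The same note frees bone marrow assessments from confirmation. It gives no such exemption for serum M-protein, urine M-protein or free light chains. Section 18.3.3.2 leaves further detail on confirmation to the reporting and analysis plan.

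**The concern.** The two documents give different rules for the same category in the same cohort, and the category acts as a stop. Under the SAP, one PD entry closes the window in which a confirmed response can be earned. Under Appendix 15, one PD entry that is not repeated does not establish progression, so later assessments still count.

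This bears on the primary endpoint. Confirmed ORR in MM enters the hierarchical model and the final rule that the posterior probability exceed 92%. A reader who relies on section 3 would believe that the SAP applies the protocol's MM criteria unchanged, and for PD it does not.

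Patients can be assessed after a first PD. Protocol section 6.7 allows treatment, with response assessments, to continue past a first progression after consultation with the Medical Lead.

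**Working it through.** There is no stated figure to reproduce. The check applies both rules to the same visit sequences.

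**Conventions.** A confirmed category is the lower of two consecutive non-PD assessments, as in Table 2-3. Under the SAP, everything from the first PD onward is discarded. Under Appendix 15, progression needs two PDs in a row; an isolated PD interrupts a run but does not end assessment. Visit entries are taken as unconfirmed readings.

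**Sequences**

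| Visits | SAP Table 2-3 | Appendix 15, note a |
|---|---|---|
| SD, PD, PR, PR | PD | confirmed PR |
| PR, PD, PR, PR | PD | confirmed PR |
| PD, PR, PR | PD | confirmed PR |
| SD, SD, PD, PR, PR | SD | confirmed PR |
| PR, PR, PD, PR | confirmed PR | confirmed PR |

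The last row shows the limit: a response already confirmed before the PD is kept under both rules.

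**Direction.** Any pair of responses before the first PD counts under both rules. Appendix 15 can add pairs after an isolated PD and removes none. SAP responders are therefore a subset of Appendix 15 responders. Enumeration agrees. Of the 3^4 = 81 four-visit sequences of PR, SD and PD, 6 are responders under Appendix 15 only and 0 under the SAP only. The six are:

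- PR-PD-PR-PR
- SD-PD-PR-PR
- PD-PR-PR-PR
- PD-SD-PR-PR
- PD-PR-PR-SD
- PD-PR-PR-PD

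This counts patterns and is not a probability.

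**Size per patient.** One reclassified patient changes ORR by 1/n. Final MM n is not in the documents. Protocol Table 32 projects 5, 17 or 20, and section 18.2.1 caps the primary analysis cohort at 25:

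- 1/5 = 20 points
- 1/17 = 5.9 points
- 1/20 = 5 points
- 1/25 = 4 points

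**Scale against the decision rule.** This is an illustration only: no borrowing, a Beta(1,1) prior and the 15% MM control, so it is not the trial's model. With k responders the posterior is Beta(1+k, 1+n−k). At n = 10, P(ORR > 15%) is 0.931 for k = 3 and 0.779 for k = 2. At n = 20 it is 0.971 for k = 6 and 0.917 for k = 5. These k were chosen at the boundary, so crossing 92% is built in. The example shows only how far one responder moves the posterior.

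**The case against.** **The practical effect may be nil.** Investigators are told to assess MM by Appendix 15, which includes note a. If they enter PD only after a second consecutive assessment, the SAP's single entry is already a confirmed PD, and asking for two entries would count confirmation twice. This stands as a possibility. The SAP does not settle it. Because it confirms the other MM categories by program, it appears to treat visit entries as unconfirmed.

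**Few patients could be affected.** The isolated PD must come before two consecutive responses, and the patient must remain under assessment. The default in protocol section 4 is to stop treatment at progression. This stands in full.

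**The direction is conservative.** A rule that can only lower ORR cannot by itself create a false claim of activity in MM. That is true, but it can still misstate the primary endpoint.

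**The protocol delegates confirmation details.** Section 18.3.3.2 does so, but leaving detail to a later plan does not permit dropping a requirement that Appendix 15 states.

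**Stronger readings that the documents do not support.**

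- *A large share of MM patients would be misclassified.* With an assumed 1% to 3% false PD per visit over 12 four-weekly visits, 1 − (1 − p)^12 gives 11% to 31%. No document gives that rate. The figure counts any false PD in 48 weeks, including those after a response is confirmed, so it is not the share of responders lost. The visit count is also uncertain: SAP section 4.2 treats MM as assessed every 8 weeks in that period.
- *MM PFS is shortened.* Table 2-3 governs best response. SAP section 2.6.2 gives progression rules for the RECIST, RANO and HCL cohorts but none specific to MM, so the effect on PFS is unknown.
- *Response assessment ends at the first PD.* Protocol section 6.7 lets it continue; the SAP stops counting it.

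**Conclusion.** The conflict is real and undeclared. For PD in MM, the SAP asks for one assessment where the protocol asks for two, with only bone marrow exempt. This should be corrected because it touches the definition of the primary endpoint.

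The consequence is conditional. If visit-level PD entries are unconfirmed, and a patient has an isolated PD before two consecutive responses and stays under assessment, that patient is lost as a responder. Each such patient lowers MM ORR by 4 to 20 points for n = 25 down to 5. How often this happens, and whether it would alter the 92% decision under the hierarchical model, cannot be determined from the documents.

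Tables 2-2 and 2-4 carry the same PD wording. The explicit two-assessment requirement for PD is in the MM appendix, so the contradiction is specific to MM.

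**What to change.** 1. Align the PD row of Table 2-3, and its bar on later responses, with note a: PD needs two consecutive assessments except where it rests on bone marrow, and assessments after an isolated PD still count.
2. State whether PD on the VISIT form already reflects two assessments. If it does, say so and do not require a second entry.
3. If single-assessment PD is preferred, declare it in SAP section 3 and report MM ORR under the Appendix 15 rule alongside.
4. State which PD definition and which date apply to MM PFS.

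Note a does not say how to treat a PD followed by death or new therapy with no further assessment, or which of two PD dates counts. It also does not say whether responses on either side of an isolated PD are consecutive: PR-PD-PR is not evaluable if the PD breaks the run and a confirmed PR if the PD is ignored. The SAP should give its choice on each and present it as its own rule.

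The cost is SAP wording and a small change to the derivation program. The Amendment 11 rationale reports no MM subject on treatment and two in follow-up as of 06-Apr-2020. The change therefore works almost entirely on recorded data, with a query to sites if item 2 cannot be answered centrally.
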